
Statistical methods:
 
For change from baseline in HbA1c up to 24 weeks of treatment a restricted maximum likelihood estimation based on a mixed-effect model for repeated measures analysis will be used to obtain adjusted means for the treatment effects on the full analysis set (FAS). This model will include treatment, visit, and the stratification factors renal function at baseline, and pretreatment with Metformin at screening as discrete fixed effects, baseline HbA1c as a continuous fixed effect, and interaction between visit and treatment, and an interaction between visit and baseline HbA1c. The primary treatment comparisons will be the contrast between treatments at the endpoint visit at 24 weeks of treatment.
 
For the change from baseline in trough seated SBP up to 12 weeks of treatment and the change from baseline in body weight in kg at 24 weeks as well a restricted maximum likelihood estimation based on mixed-effect models for repeated measures analysis will be used to obtain adjusted means for the treatment effects on the FAS. These models will include the same discrete fixed effects as the model for the primary endpoint and baseline HbA1c as continuous fixed effect, as well as interaction between visit and treatment, and interaction between visit and baseline measurement of the key secondary endpoint, as well as the corresponding baseline measurements of the key secondary endpoint as continuous effect. The primary treatment comparisons will be the contrast between treatments at the 12 week visit for seated SBP and 24 week visit for body weight.
 
The key secondary endpoint change from baseline in 24-hour ambulatory SBP and change from mean trough ambulatory SBP at 12 weeks will be analyzed by using an analysis of covariance (ANCOVA) approach in the FAS with last observation carried forward (LOCF) for missing data. The model will include randomised treatment, renal function at baseline, pretreatment with Metformin at screening as discrete fixed effects and the baseline of the key secondary endpoint and HbA1c at baseline as continuous fixed effects.
 
The overall type I error across the hypotheses tests in the confirmatory analysis will be maintained at a level of $\alpha \leq 0.05$ using a hierarchical testing sequence. The sample size of 154 patients per group was derived (assuming n=64 per groups plus a 20% drop-out rate) based on the requirement that the comparisons of empagliflozin versus placebo with respect to the HbA1c, BP and body weight should have a power of at least 80% at the two-sided α level of 5%.
 
Explorative statistical models and descriptive statistics will be used for the other secondary endpoints and safety parameters.
			

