7.2 NULL AND ALTERNATIVE HYPOTHESES

Primary Hypotheses

The confirmatory analyses will compare empagliflozin to placebo. The following hierarchical multiple testing procedure will be used to evaluate superiority for the primary endpoint followed by the evaluation of superiority of the key secondary endpoints, while maintaining the overall probability of a type I error at 0.05. The primary endpoint of change from baseline to 24 weeks in HbA1c along with the key secondary endpoints change from baseline in mean 24-hour ambulatory SBP at 12 weeks of treatment, change from baseline in mean trough ambulatory SBP at 12 weeks of treatment, change from baseline in body weight in kg at week 24 of treatment, and change from baseline in trough seated SBP at 12 weeks of treatment, will be tested in the following pre-specified hierarchical sequence, to address issues of multiplicity. Proceeding onto the next step in the sequence relies upon rejecting H_0 in the previous step, a 'success'. Each step will only be considered confirmatory if all previous steps were 'successful'. If any of the previous steps were not successful, the tests of the subsequent steps have to be interpreted in an exploratory sense. This procedure allows testing each step at the two-sided alpha-level of 5%:

1. change from baseline in HbA1c at 24 weeks of treatment
2. change from baseline in mean 24-hour ambulatory SBP at 12 weeks of treatment
3. change from baseline in mean trough ambulatory SBP at 12 weeks of treatment
4. change from baseline in body weight in kg at week 24 of treatment
5. change from baseline in trough seated SBP at 12 weeks of treatment

Proprietary confidential information.

© 2016 Boehringer Ingelheim International GmbH or one or more of its affiliated companies. All rights reserved.

This document may not - in full or in part - be passed on, reproduced, published or otherwise used without prior written permission.

At each of the 5 stages of the hierarchical sequence the hypotheses will be tested as described below:

$H_{0,1}$: No difference in mean endpoint between empagliflozin and placebo

$H_{1,1}$: A difference in mean endpoint between empagliflozin and placebo

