7.6 DETERMINATION OF SAMPLE SIZE

In order to ensure that each comparisons of empagliflozin and placebo with respect to HbA1c, mean systolic ABPM blood pressure and body weight have a power of at least 80%, 64 patients plus an additional 20% drop-out rate, resulting in 77 patients per arm are required per treatment group. This is derived from the assumption that the difference in change from baseline compared to placebo in 24-hour SBP is 5 mmHg with a standard deviation of 10

Proprietary confidential information.

© 2016 Boehringer Ingelheim International GmbH or one or more of its affiliated companies. All rights reserved.

This document may not - in full or in part - be passed on, reproduced, published or otherwise used without prior written permission.

mmHg (resulting in a power of 80%), and the difference in body weight is 2 kg with a standard deviation of 2.3kg (resulting in a power of 99%). With this sample size the power to detect a 0.6% difference in HbA1c with a standard deviation of 1.1% will be >85%.

The planned treatment group sizes are considered as sufficient for the confirmatory evaluation of efficacy and the descriptive assessment for safety, tolerability and PK.

Proprietary confidential information.

© 2016 Boehringer Ingelheim International GmbH or one or more of its affiliated companies. All rights reserved.

This document may not - in full or in part - be passed on, reproduced, published or otherwise used without prior written permission.

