7.4 PRIMARY ENDPOINT(S)

7.4.1 Primary efficacy analysis

A hierarchical multiple testing procedure will be used to evaluate superiority of the primary endpoint, followed by the evaluation of superiority of the key secondary endpoints in the following pre-specified hierarchical sequence:

- I. Primary endpoint: Change from baseline in HbA_{1c} (%) at week 24
- II. Key secondary endpoint: Change from baseline in mean 24-hour ambulatory SBP (mmHg) at week 12
- III. Key secondary endpoint: Change from baseline in mean trough ambulatory SBP (mmHg) at week 12
- IV. Key secondary endpoint: Change from baseline in body weight (kg) at week 24

- V. Key secondary endpoint: Change from baseline in trough seated SBP (mmHg) at week 12

Each step will be considered confirmatory if all previous steps were successful (superiority was achieved). If any of the previous steps were unsuccessful, the subsequent steps are regarded as exploratory.

The primary analysis is at 24 weeks and will be performed on the FAS (OC). It is a restricted maximum likelihood (REML)-based mixed model repeated measures (MMRM) approach comparing the change from baseline in HbA_{1c} after 24 weeks of treatment. Missing data are handled directly by the fitted model. According to published literature, MMRM analysis appears to be a superior approach for controlling Type I error rates and minimizing bias as compared to single imputation approaches such as LOCF ANCOVA analysis particularly in the presence of missing completely at random (MCAR) or missing at random (MAR) data (4).

The statistical model will be:

[figure not shown]
$$\text{HbA}_{1c} \text{ change from baseline at each on-treatment visit} = \text{overall mean} + \text{HbA}_{1c} \text{ baseline} + \text{treatment} + \text{renal function} + \text{pretreatment with metformin} + \text{visit} + \text{visit by treatment interaction} + \text{visit by HbA}_{1c} \text{ baseline interaction} + \text{random error}$$

[figure not shown]

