7.5 SECONDARY ENDPOINT(S)

7.5.1 Key secondary endpoint(s)

The key secondary endpoints for this study are described in [Section 5.2](#).

For the following key secondary endpoints:

- Change from baseline in mean 24-hour ambulatory SBP at week 12
- Change from baseline in trough mean ambulatory SBP at week 12

ANCOVAs will be performed based on the FAS (LOCF-H), [REDACTED]

[REDACTED] The respective model will include treatment, renal function, pretreatment with metformin, continuous baseline HbA_{1c} and continuous baseline of the respective secondary endpoint.

[figure not shown]
The results from these analyses will be presented graphically as for the descriptive values. As ambulatory measurements only provide one post-baseline assessment until week 12 (i.e. no repeated measurements), MMRM models will not be applied for these endpoints.

MMRM will be performed for the remaining key secondary endpoints (to be tested as third and fourth key secondary endpoints, respectively):

- change from baseline in body weight at week 24
- change from baseline in trough seated SBP at week 12

based on the FAS (OC) or FAS (OC-H), [REDACTED]

[REDACTED]. The model will be the same as that defined for the primary efficacy analysis with the addition of the continuous baseline key secondary endpoint as a covariate and visit by continuous baseline key secondary endpoint interaction.

Summary of hierarchical testing strategy for confirmatory analysis for superiority testing of treatment effect of Empa vs. Placebo (each step is tested at the two-sided alpha-level of 5%):

- I. Primary endpoint: Change from baseline in HbA_{1c} (%) at week 24
 - Primary analysis: MMRM on FAS (OC)
- II. Key secondary endpoint: Change from baseline in mean 24-hour ambulatory SBP (mmHg) at week 12
 - ANCOVA on FAS (LOCF-H)
- III. Key secondary endpoint: Change from baseline in mean trough ambulatory SBP (mmHg) at week 12
 - ANCOVA on FAS (LOCF-H)
- IV. Key secondary endpoint: Change from baseline in body weight (kg) at week 24
 - MMRM on FAS (OC)
- V. Key secondary endpoint: Change from baseline in trough seated SBP (mmHg) at week 12
 - MMRM on FAS (OC-H)

7.5.2 (Other) Secondary endpoint(s)

[figure not shown]
The other secondary efficacy endpoints for this study are specified in [Section 5.2.2](#).

[figure not shown]

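### Does the 99% power for body weight mislead, given that body weight is tested fourth in a fixed sequence?

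*Protocol*

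**What the plan says.** Protocol 7.6 sizes the trial to "ensure that each comparisons of empagliflozin and placebo with respect to HbA1c, mean systolic ABPM blood pressure and body weight" have at least 80% power, using 64 patients per arm, raised to 77 for drop-out. Its inputs are 5 mmHg (SD 10) for 24-hour SBP, with a stated power of 80%, and 0.6% (SD 1.1%) for HbA1c, with a stated power of >85%. For weight, it says that "the difference in body weight is 2 kg with a standard deviation of 2.3kg (resulting in a power of 99" per cent. It then concludes: "The planned treatment group sizes are considered as sufficient for the confirmatory evaluation of efficacy".

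The synopsis, under Statistical methods, describes the hierarchical sequence and in the next sentence asks that the comparisons "with respect to the HbA1c, BP and body weight should have a power of at least 80" per cent.

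Protocol 7.2 fixes the order: HbA1c, 24-hour ambulatory SBP, trough ambulatory SBP, body weight, trough seated SBP. "Each step will only be considered confirmatory if all previous steps were" successful; otherwise later tests are exploratory. SAP 7.4.1 says the same: "Each step will be considered confirmatory if all previous steps were successful (superiority was achieved"). SAP 7.5.1 places body weight and trough seated SBP last, "to be tested as third and fourth key secondary endpoints, respectively".

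Neither document gives the power to reach and pass a given step. Section 7.6 gives no effect or SD for trough ambulatory SBP.

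**The concern.** In a fixed sequence, the power of a later test taken alone is not the chance that it yields a confirmatory result. A reader who takes 99% as the prospect of a confirmatory weight claim would be too optimistic, since that claim first has to pass a 24-hour SBP test planned at 80%. Section 7.6 moves from per-comparison power to a statement about the confirmatory evaluation without mentioning the sequence, and the synopsis puts the two side by side. At stake is what readers expect of the key secondary endpoints. Type I error and the primary HbA1c test are not in question.

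**Working it through.** **Inputs.** Effects, SDs and 64 or 77 per arm come from Protocol 7.6. Two-sided alpha of 0.05 at each step and the order of testing come from Protocol 7.2. Allocation of 1:1 comes from Protocol 7.5.

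**Step 1: the plan's own figures.** For a two-sample t-test with n per arm, the noncentrality is δ / (SD × √(2/n)) on 2n − 2 degrees of freedom.

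| Comparison | δ / SD | Noncentrality, n = 64 | Power, n = 64 | Power, n = 77 | Stated in 7.6 |
|---|---|---|---|---|---|
| HbA1c | 0.6 / 1.1 | 3.09 | 86.5% | 92.0% | >85% |
| 24-hour SBP | 5 / 10 | 2.83 | 80.1% | 86.9% | 80% |
| Body weight | 2 / 2.3 | 4.92 | 99.8% | 99.97% | 99% |

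All three stated values hold at 64 analysed per arm.

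**Step 2: confirmatory body weight.** This requires steps 1 to 4 all to reject. A joint probability cannot exceed its smallest component:

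- n = 64: at most min(0.865, 0.801, 0.998) = 0.801
- n = 77: at most min(0.920, 0.869, 0.9997) = 0.869

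The bound holds for any correlation between the tests. It counts no further loss at the HbA1c and trough ambulatory SBP steps. As an illustration only, if trough SBP had the same power as 24-hour SBP and all tests were independent, weight would have 0.865 × 0.801 × 0.801 × 0.998 ≈ 0.55 at 64 per arm, and about 0.69 at 77.

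**Step 3: confirmatory 24-hour SBP.** This requires steps 1 and 2 to reject. With powers p₁ and p₂, the joint probability is p₁p₂ under independence and at most min(p₁, p₂). The values at correlation 0.5 come from a bivariate normal distribution with these margins.

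| n per arm | Independent | Correlation 0.5 | Upper bound |
|---|---|---|---|
| 64 | 0.865 × 0.801 = 0.693 | 0.731 | 0.801 |
| 77 | 0.920 × 0.869 = 0.799 | 0.822 | 0.869 |

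The lower bound over every possible dependence, p₁ + p₂ − 1, is 0.666 at 64 and 0.789 at 77. Values below the independence figure need negative correlation between the two tests, so about 69–80% (64) and 80–87% (77) are the ranges for non-negative correlation.

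**Step 4: how firm the cap is.** Steps 2 and 3 use an unadjusted test. Protocol 7.3.1 and SAP 7.5.1 plan an ANCOVA with baseline SBP and baseline HbA1c as covariates, and the documents do not say whether SD 10 is before or after adjustment. If it is before adjustment, and the covariates have correlation r with the outcome, the residual SD is 10 × √(1 − r²):

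| r (assumed) | Residual SD | SBP power, n = 64 | SBP power, n = 77 |
|---|---|---|---|
| 0.3 | 9.54 | 83.7% | 89.8% |
| 0.5 | 8.66 | 90.0% | 94.5% |

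At r = 0.5, SBP would no longer be the limiting step; HbA1c at its unadjusted 86.5% (64) or 92.0% (77) would be. In the other direction, a true 20% loss from 77 leaves 77 × 0.8 = 61.6 per arm, where unadjusted SBP power is 78.6%.

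**The case for a change.** The strongest case for a change is that the weight cap follows from logic and the plan's own inputs. At 64 per arm, the chance of missing a confirmatory weight result is at least about 20%, not about 1%. Section 7.6 does speak of the confirmatory evaluation, which Protocol 7.2 defines by the sequence. Without a trough ambulatory SBP assumption, no reader can complete the weight figure. The remedy would be a sentence and one stated assumption.

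The arithmetic stands, and so does the observation that power under the sequence is not given. What does not follow is that anything stated is wrong. Section 7.6 names its target as per comparison and states the 64, so relabelling the figures would repeat what is there. Calling the group sizes sufficient is a qualitative judgement, and two neighbouring synopsis sentences do not amount to a claim of joint power. A reader who knows the sequence from Protocol 7.2 can see that 24-hour SBP must succeed before weight, and can read the limit from the 80% printed next to the 99%. Stating a flat cap in the protocol would also bring in a figure that depends on an unadjusted test the trial will not use.

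**Conclusion.** No change is needed. The 80%, 99% and >85% are correct per-comparison powers and are presented as such. With the 7.6 inputs and an unadjusted test, a confirmatory weight result has at most about 80% power (64 per arm) or 87% (77 per arm). A confirmatory 24-hour SBP result has about 69–80% or 80–87%, provided its correlation with the HbA1c test is not negative. Covariate adjustment could raise these figures, while loss at the trough ambulatory SBP step would lower the weight figure by an amount the plan does not allow one to compute.

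This is missing detail on the prospects of secondary claims. The tests, their order, the sample size, the type I error and the reading of any result are the same with or without it. A sentence in 7.6 giving the conditional figures would be a courtesy to readers, but it would not improve the trial's conclusions.

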8. INFORMED CONSENT, DATA PROTECTION, TRIAL RECORDS

The trial will be carried out in compliance with the protocol, the principles laid down in the Declaration of Helsinki, in accordance with the ICH Harmonised Tripartite Guideline for GCP and relevant BI SOPs. Standard medical care (prophylactic, diagnostic and therapeutic procedures) remains in the responsibility of the treating physician of the patient.

The investigator should inform the sponsor immediately of any urgent safety measures taken to protect the study subjects against any immediate hazard, and also of any serious breaches of the protocol/ICH GCP.

The rights of the investigator and of the sponsor with regard to publication of the results of this trial are described in the investigator contract. As a general rule, no trial results should be published prior to finalisation of the CTR.

Insurance Cover: The terms and conditions of the insurance cover are made available to the investigator and the patients via documentation in the ISF.

8.1 STUDY APPROVAL, PATIENT INFORMATION, AND INFORMED CONSENT

This trial will be initiated only after all required legal documentation has been reviewed and approved by the respective IRB/ Independent Ethics Committee (IEC) and competent authority (CA) according to national and international regulations. The same applies for the implementation of changes introduced by amendments.

Prior to patient participation in the trial, written informed consent must be obtained from each patient (or the patient's legally accepted representative) according to ICH GCP and to the regulatory and legal requirements of the participating country. Each signature must be personally dated by each signatory and the informed consent and any additional patient-information form retained by the investigator as part of the trial records. A signed copy of the informed consent and any additional patient information must be given to each patient or the patient's legally accepted representative.

The respective procedure for illiterate patients (if included) is described in the [Appendix 10.1](#).

The patient must be informed that his/her personal trial-related data will be used by BI in accordance with the local data protection law. The level of disclosure must also be explained to the patient.

The patient must be informed that his / her medical records may be examined by authorised monitors (CML/CRA) or Clinical Quality Assurance auditors appointed by BI, by appropriate IRB / IEC members, and by inspectors from regulatory authorities.

Proprietary confidential information.

© 2016 Boehringer Ingelheim International GmbH or one or more of its affiliated companies. All rights reserved.

This document may not - in full or in part - be passed on, reproduced, published or otherwise used without prior written permission.

8.2 DATA QUALITY ASSURANCE

In order to achieve a high level of standardised processes, data collection of efficacy and safety endpoints is coordinated centrally:

- central lab analysis of efficacy endpoints, biomarkers and safety lab
- central IRT system for stratification, randomisation and kit allocation at each visit
- Central hepatic adjudication assessment

The data management procedures to ensure the quality of the data are described in detail in the trial data management and analysis plan available in TMF.

A quality assurance audit/inspection of this trial may be conducted by the sponsor or sponsor's designees or by IRBs/IECs or by regulatory authorities. The quality assurance auditor will have access to all medical records, the investigator's trial-related files and correspondence, and the informed consent documentation of this clinical trial.

8.3 RECORDS

Case Report Forms (CRFs) for individual patients will be provided by the sponsor, either on paper or via RDC. See [Section 4.1.5.2](#) for rules about emergency code breaks. For drug accountability, refer to [Section 4.1.8](#).

8.3.1 Source documents

Source documents provide evidence for the existence of the patient and substantiate the integrity of the data collected. Source documents are filed at the investigator's site.

Data entered in the eCRFs that are transcribed from source documents must be consistent with the source documents or the discrepancies must be explained. The investigator may need to request previous medical records or transfer records, depending on the trial; also current medical records must be available.

For eCRFs all data must be derived from source documents.

8.3.2 Direct access to source data and documents

The investigator / institution will permit trial-related monitoring, audits, IRB / IEC review and regulatory inspection, providing direct access to all related source data / documents. CRFs/eCRFs and all source documents, including progress notes and copies of laboratory and medical test results must be available at all times for review by the sponsor's clinical trial monitor, auditor and inspection by health authorities (e.g. FDA). The CRA/ on site monitor and auditor may review all CRFs/eCRFs, and written informed consents. The accuracy of the data will be verified by reviewing the documents described in Section 8.3.1.

Proprietary confidential information.

© 2016 Boehringer Ingelheim International GmbH or one or more of its affiliated companies. All rights reserved.

This document may not - in full or in part - be passed on, reproduced, published or otherwise used without prior written permission.

8.4 LISTEDNESS AND EXPEDITED REPORTING OF ADVERSE EVENTS

8.4.1 Listedness

To fulfil the regulatory requirements for expedited safety reporting, the sponsor evaluates whether a particular adverse event is "listed", i.e. is a known side effect of the drug or not. Therefore a unique reference document for the evaluation of listedness needs to be provided. For the empagliflozin this is: the current version of the IB [c01678844](#). The current version of this reference document is to be provided in the ISF. No AEs are classified as listed for matching placebo.

8.4.2 Expedited reporting to health authorities

BI is responsible to fulfil their legal regulatory reporting obligation and in accordance to the requirements defined in this CTP.

